6.6. Subgroup Analyses

Subgroup analyses of the MFS endpoint for both enzalutamide in combination with leuprolide versus placebo in combination with leuprolide and enzalutamide monotherapy versus placebo in combination with leuprolide will be performed to determine whether the treatment effect is concordant among subgroups. If the subgroups are too small (<10 events), the analyses would not be provided. The unstratified hazard ratios and their 95% confidence intervals will be displayed in a forest plot. The following variables defined by baseline subject characteristics will be used to define subgroups:

- PSA doubling time (≤ 3 months, >3 to ≤ 6 months, >6 to ≤ 9 months);
- Baseline use of a bone targeting agent (yes, no);
- Baseline age category at baseline ($<65, \ge 65$);
- Race (African-American or Black, White, Other);
- Body mass index calculated from height and weight (at or below median, above median);
- ECOG performance status at baseline (0, 1);
- Geographic region (North America, Europe, and rest of the world);
- Total Gleason score at baseline ($\leq 7, \geq 8$) at diagnosis;
- Prior neoadjuvant/adjuvant hormonal therapy (yes, no);
- Prior radiation therapy (yes, no);
- Prior prostatectomy (yes, no);

- History of cardiovascular disease (yes, no);
- PSA value at baseline ($\leq 10 \text{ ng/mL}$, >10 ng/mL);

6.7. Baseline and Other Summaries and Analyses

6.7.1. Baseline Summaries

Demographic and Baseline Characteristics

The following demographic and baseline characteristics will be summarized by treatment group as randomized for all patients in the ITT population and by geographic region:

- Age, race, weight, and body mass index;
- Geographic region (North America, Europe, rest of world) (Appendix 1);
- Categorized screening PSA doubling time (≤3 months ,>3 to ≤6 months, and >6 to ≤9 months), and continuous screening PSA doubling time;
- Prior neoadjuvant/adjuvant hormonal therapy (yes, no) and/or short course of hormonal therapy (yes, no);
- Prior prostatectomy (yes, no);
- Prior radiation therapy (yes, no);
- Prior prostatectomy and radiation therapy (yes, no);
- Eastern Cooperative Oncology Group (ECOG) performance status;
- Baseline serum PSA (≤10 ng/mL, >10 ng/mL), and continuous baseline serum PSA (ng/mL);
- History of cardiovascular disease (yes, no).

Listings will be provided for these parameters for all randomized patients.

Disease Characteristics

The following medical history and disease characteristics will be summarized by treatment group as randomized for all patients in the ITT population:

- Time (months) from initial pathological diagnosis or first treatment for prostate cancer to randomization, whichever is earlier;
- Total Gleason score category at diagnosis (Low [2–4], Medium [5–7], and High [8-10]);
- Clinical Stage (T1, T2, T3);

- Pathologic tumorurgical stage;
- Lymph node stage;
- Pelvic soft tissue lesion(s);

Previous Therapies

Previous therapies for prostate cancer will be summarized by treatment group as randomized for all patients in the ITT population as follows:

- Number of prior prostate cancer therapies;
- Number of prior hormonal therapies;
- Prior nonhormonal therapy use (yes/no);
- Use of bisphosphonate or denosumab for non-prostate cancer therapy (yes/no) at baseline;
- History of surgical prostate cancer procedures (yes/no).

6.7.2. Study Conduct and Patient Disposition

Study conduct will be summarized by randomized treatment group as follows:

- Randomized patients by randomization stratification factors;
- Reason for exclusion from 1 or more populations;

Patients Disposition will be summarized as follows:

- Patients discontinuing treatment and the reasons for discontinuation (as documented on the case report form (CRF), including death, lost to follow-up, protocol violation, withdrew consent to continue treatment, disease progression, adverse event, or other);
- Patients withdrawing from long-term follow-up and the reasons for withdrawal.

The number of patients in each of the specified populations (ITT, eITT, safety) will be provided. Additionally, the number and percentage of patients on treatment and in follow-up will be provided for the safety population.

The following listings will be produced:

- Patients who received treatment different from the treatment randomized;
- Patients discontinuing from each study period after enrollment (study center, treatment group, reason, dose of enzalutamide, and the duration of treatment).

6.7.3. Protocol Deviations

Patients with major protocol deviations will be listed and summarized by treatment group as randomized. Categories of major deviations are as follows but not limited to:

- Eligibility criteria were not met
- Developed criteria for discontinuation of study drug but did not discontinue study treatment
- Received excluded concomitant medication
- Received the wrong treatment or incorrect dose
- Did not sign informed consent before study-specific procedures were performed

A detailed list of all major protocol deviations will be determined before the study is unblinded and a listing of all major deviations will be provided.

6.7.4. Study Treatment Exposure

Data from patients in the safety population will be used to summarize exposure and compliance.

Enzalutamide

The summary of treatment exposure for enzalutamide will include the following information:

- Treatment duration (months)
- Treatment suspension duration (months)
- Modified treatment duration (months)
- Duration of treatment after reinitiation (months)
- Cumulative dose (mg)
- Average daily dose (mg/day).

Treatment duration, treatment suspension duration, modified treatment duration and duration of treatment after reinitiation (see Section 5.2.5) will be summarized both as a continuous measures and as categorical measures (≤ 6 months, 6 to <12 months, 12 to <24, 24 to <36, 36 to <48, 48 to <60, 60 to <72, and ≥ 72 where appropriate).

The cumulative dose is the sum of the actual dose levels that the patient received (ie, total dose administered).

Average daily dose is the cumulative dose divided by the modified treatment duration.

The total number of capsules taken and percent overall compliance will also be summarized. Number of capsules taken will be calculated based on the number of capsules dispensed at all study visits minus the number of capsules indicated as returned. The total cumulative dose in milligrams (mg) will be calculated as (40 mg \times number of capsules taken), as each capsule is equivalent to 40 mg of the study drug or placebo.

Percent overall compliance rate will be defined as the number of capsules taken during the study divided by the expected number of capsules, multiplied by 100. Capsules from bottles not returned will be subtracted from the number of capsules taken and the expected number of capsules in calculating percent overall compliance rate. Each patient will be taking 4 capsules each day while on study treatment. A patient's expected number of capsules will be calculated as $[4 \times (\text{date of last dose prior to data cutoff date – date of first dose of study drug + 1)]$. However, for patients who have dose modifications (eg, dose reduction or dose withholding, or drug suspension due to undetectable PSA), the expected number of capsules will be summarized both as a continuous measure and a categorical measure in increments of 20%.

A data listing will be provided to present dose administration, modifications, and the derived compliance variables.

Dose Reduction and Modification

A dose reduction is defined as a non-zero dose that is less than the prior dose.

The number and percentage of patients with at least 1 dose reduction as well as a breakdown of dose reductions $(1/2/3/\geq 4)$ will be summarized by treatment arm.

Reasons for dose reductions will also be summarized. Patients can contribute to more than 1 reason if multiple dose reductions occurred for different reasons, but will only be counted once per reason. Percentages will be calculated based on the total number of patients in safety analysis set.

An interruption is defined as a 0 mg dose administered on 1 or more days (not including the treatment suspension period due to undetectable PSA at week 36). The number and percentage of patients with at least 1 dose interruption will be summarized by treatment arm.

Reasons for dose interruption will also be summarized. Patients can contribute to more than 1 reason if multiple dose interruptions occurred for different reasons, but will only be counted once per reason. Percentages will be calculated based on the total number of patients in safety analysis set.

Leuprolide

Number of injections before and after the suspension period by treatment arms will be summarized. A summary of the number of missed injections will also be provided.

A data listing will be provided to present the number of treatments, dose administration, route of treatment (subcutaneous or intramuscular injection) and modifications for leuprolide.

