6.4. Treatment Compliance

Accountability for the study drug capsules (enzalutamide, placebo) will be performed to document compliance with the dosing regimens. Patients will be asked to bring all study drug including empty bottles to study visits. Study site personnel must make reasonable efforts to obtain study drug from patients who do not routinely return them at study site visits. Unreturned capsules will be considered to have been taken.

Compliance with leuprolide treatment will be determined by testosterone suppression.

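### SAP 6.7.4 miscalculates compliance when unreturned bottles still hold unused capsules, and its two definitions of cumulative dose then disagree

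*SAP*

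**What the plan says.** SAP 6.7.4 (Study Treatment Exposure) sets these rules for the capsules:

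- **Capsules taken** are "the number of capsules dispensed at all study visits minus the number of capsules indicated as returned". A capsule that never comes back is therefore credited as swallowed.
- **Cumulative dose, in words:** "The cumulative dose is the sum of the actual dose levels that the patient received". The next statement is "Average daily dose is the cumulative dose divided by the modified treatment duration".
- **Cumulative dose, as a formula:** "The total cumulative dose in milligrams (mg) will be calculated as (40 mg", multiplied by capsules taken. No deduction is made for unreturned bottles.
- **Compliance** is capsules taken over capsules expected, times 100, with this adjustment: "Capsules from bottles not returned will be subtracted from the number of capsules taken and the expected number of capsules". The adjustment applies to the compliance rate only.
- **Expected capsules** are 4 for each day from the first dose to the last dose before data cutoff.

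SAP 5.2.5 also ends treatment duration at the last dose. Protocol 6.4 has a different convention: "Unreturned capsules will be considered to have been taken". Protocol 10.6 defines compliance with no deduction for unreturned bottles.

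The SAP sentence on expected capsules after a dose modification or suspension is broken in the text available. Nothing below depends on it.

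**The concern.** Taking the same quantity out of a numerator and a denominator is sound only if it was in both. Unused capsules in an unreturned bottle are in the numerator, because dispensed minus returned credits them as taken. They are not in the denominator, because the expected count stops at the last dose. The adjustment removes them from both sides, so the denominator becomes too small.

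The same unused capsules enter the 40 mg formula as drug taken, while the duration they are divided by stops at the last dose. The worded definition, based on dose levels actually received, leaves them out. The two definitions in one section therefore give different cumulative doses, and different average daily doses, for the same man.

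At stake is whether the compliance and exposure tables can be read at face value. Means and the 20% compliance categories would contain values that cannot be true.

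**Working it through.** **Inputs.** Four 40 mg capsules per day, 160 mg/day (SAP 2.2). Each dispensing visit gives a 12-week supply (Protocol 5.2), so 84 × 4 = 336 capsules. Bottle size is not stated, so the main cases treat the whole latest supply as unreturned. The documents give no compliance or average-dose result to reproduce.

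**Formulas.** Let D = dispensed, R = returned, U = capsules dispensed in bottles not returned, u = those swallowed from these bottles, t = days from first to last dose, with no week-37 suspension.

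- Compliance = 100 × (D − R − U) / (4t − U)
- Average daily dose under the 40 mg formula = 40 × (D − R) / t

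For a fully adherent man these reduce to (4t − u)/(4t − U) and 160 + 40(U − u)/t. Both are right only when U = u, that is, when the missing bottles were empty.

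**Cases where the rules work.**

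- All leftovers returned, stop at day 100: D = 672, R = 272, U = 0; 400/400 = 100% and 16,000/100 = 160 mg/day.
- First supply used up and its bottles lost, 296 capsules returned from the second, stop at day 94: (376 − 336)/(376 − 336) = 100%.

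**Cases where they fail.** Perfect dosing, latest supply wholly unreturned, R = 0. The true values are always 100% and 160 mg/day.

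| Last dose (day) | D | 4t | Compliance | Average daily dose, 40 mg formula |
|---|---|---|---|---|
| 10 | 336 | 40 | 0/(−296) | 13,440/10 = 1,344 mg |
| 84 (supply just used up) | 336 | 336 | 0/0 | 13,440/84 = 160 mg |
| 94 | 672 | 376 | 336/40 = 840% | 26,880/94 = 286 mg |
| 126 | 672 | 504 | 336/168 = 200% | 26,880/126 = 213 mg |
| 150 | 672 | 600 | 336/264 = 127% | 26,880/150 = 179 mg |
| 168 (supply just used up) | 672 | 672 | 336/336 = 100% | 26,880/168 = 160 mg |
| 351 (15 days into supply 5) | 1,680 | 1,404 | 1,344/1,068 = 125.8% | 67,200/351 = 191.5 mg |
| 1,023 (15 days into supply 13) | 4,368 | 4,092 | 4,032/3,756 = 107.3% | 174,720/1,023 = 170.8 mg |

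At day 94 the dose-level definition gives 376 × 40 = 15,040 mg, or 160 mg/day; the 40 mg formula gives 26,880 mg.

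**Imperfect adherence.** A man takes 90% of his capsules and stops at day 100, with 34 returned from supply 1 and supply 2 unreturned: (672 − 34 − 336)/(400 − 336) = 302/64 = 472%, and 40 × 638/100 = 255.2 mg/day.

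**Only some bottles missing.** Assume three 112-capsule bottles and a stop at day 40. With bottles 2 and 3 unreturned: (336 − 224)/(160 − 224) = 112/(−64) = −175%. With only bottle 2 unreturned and bottle 3 returned full: (224 − 112)/(160 − 112) = 112/48 = 233%.

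**Protocol rule alone.** Counting unreturned capsules as taken with no subtraction gives 672/376 = 179% at day 94, so reverting to Protocol 6.4 does not cure the problem.

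**The case against.** The strongest reply is that this is a narrow defect in descriptive tables. Much of that stands.

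- A reader might infer that every man who stops mid-supply is miscounted. He is not: if he returns his bottles, or the missing ones were empty, the result is right.
- A reader might infer that the SAP will report averages above 160 mg/day, or that these would signal overdose. The excess arises only under the 40 mg formula. The average-dose sentence directly follows the dose-level definition, under which this mechanism cannot exceed 160 mg/day. Protocol 8.5.4.1.1 defines overdose by a dose above the specified one; a derived average in an exposure table is not such a dose.
- A reader might infer that men who stop abruptly keep their bottles more often, or that the arms differ. The documents give no rate and no reason to expect imbalance. They ask sites to retrieve drug (Protocol 6.4) and repeat accountability at safety follow-up (Protocol 5.4).
- A reader might call the departure from Protocol 6.4 an error in itself. SAP Section 2 allows the SAP to modify protocol plans and promises an amendment only for major changes to the primary endpoint or its analysis.
- Medians are reported and per-patient compliance is listed, so extreme values would be seen.

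The reply does not remove the defect. SAP 6.7.4 has no cap, and no rule for a negative denominator. SAP 5.3 covers statistics that cannot be calculated, such as 0/0, but not 840% or −175%. The two cumulative-dose definitions remain unreconciled.

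**Conclusion.** The compliance rule is wrong as written for men whose unreturned bottles still hold unused capsules at the last dose, and only for them. If the whole latest supply is missing and dosing was perfect, the reported value is 840% at day 94 and 200% at day 126. With one supply dispensed and unreturned, the denominator is zero or negative. The error falls as treatment lengthens, to 107.3% at 15 days into supply 13. It is not always smaller when only some bottles are missing: in the assumed day-40 case, two missing bottles give −175%.

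Separately, cumulative dose has two definitions that disagree in these same men. Whether the average daily dose is inflated (286 mg/day at day 94) depends on which one is programmed.

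The sizes rest on a 336-capsule supply, no suspension and, where stated, an assumed 112-capsule bottle. How many men are affected cannot be judged from the documents. MFS, OS, alpha and power are untouched. The point deserves correction because the text, followed exactly, yields impossible values.

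**What to change.** In SAP 6.7.4:

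1. For unreturned bottles, keep removing their capsules from the numerator, but remove from the denominator only the capsules due from those bottles up to the last dose. Set compliance to missing (not evaluable) when no expected capsules remain.
2. Use one definition of cumulative dose, the sum of actual dose levels from the dosing records, for both cumulative and average daily dose. Drop the 40 mg × (dispensed minus returned) formula for these outputs.
3. Optionally, state that this convention replaces the Protocol 6.4 rule on unreturned capsules.

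Check: at day 94 the second supply was due to provide 4 × 10 = 40 capsules, so compliance is 336/(376 − 40) = 100%. For the 90% adherent man at day 100 it is 302/(400 − 64) = 89.9%. At day 10, 40 − 40 leaves nothing expected, so the value is missing.

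The cost is SAP wording and minor reprogramming. Step 1 needs a stated order of use, for example supplies used in the order dispensed, and bottle size where only part of a supply is missing. Step 2 uses dosing records that the SAP already needs for its interruption, reduction and listing outputs. The downside is missing compliance for a few patients.

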6.7.5. Concomitant Medications

Concomitant medications taken during the study treatment period will be summarized for all patients in the safety population by treatment group. Medications are considered concomitant if exposure occurs during the on-treatment period. Medications will be summarized by WHO drug dictionary anatomical therapeutic chemical (ATC) classification system and generic medication name.

In addition, subsequent antineoplastic therapies will be summarized separately by treatment group. Medications will be summarized by WHO drug dictionary ATC classification system and generic medication name.

All medications recorded on the case report form will be listed.

6.8. Safety Summaries and Analyses

All patients in the safety population will be used in the safety analyses. Safety analyses will be summarized by treatment group.

The on-treatment period will be defined as in Section 5.2.5. For incomplete date of last dose of study drug and incomplete start date of the first new antineoplastic treatment that are missing the day of the month, please refer to the missing data Section 5.3.1.

At the time of analyses after protocol amendment #5, safety data for the patients treated in protocol defined open-label (OL) stage will be summarized by double blinded stage and OL stage separately.

At the time of analyses after protocol amendment #5, based on the protocol defined data collection, safety will be evaluated by the frequency of serious adverse events, frequency and severity of adverse events, frequency of study drug discontinuation due to adverse events, and frequency of new clinically significant changes in clinical laboratory values and vital signs.

6.8.1. Adverse Events

The severity of all adverse events is to be evaluated by the investigator based on the NCI CTCAE version 4.03. All adverse events will be coded to preferred term (PT) and system organ class (SOC) using MedDRA version in use at the time of database release.

TEAEs will be summarized by PT and/or SOC, toxicity grade, and relationship to study treatment. An event will be considered treatment related if the investigator considered the event related to one or both of study drugs given in combination. The treatment related summaries will be separated for one or both study drugs when given in combination.

Separate summaries will be provided for serious TEAEs regardless of causality and serious TEAE related to study treatment.

Separate summaries will be provided for TEAEs (regardless of relationship to study treatment):

- Leading to permanent discontinuation from enzalutamide,
- Leading to permanent discontinuation form leuprolide,
- Leading to enzalutamide dose interruptions,
- Leading to leuprolide dose interruptions,
- Leading to enzalutamide dose reductions, and
- Leading to leuprolide dose reductions.

mTEAEs and rTEAEs defined as in Section 3.5 will be summarized by toxicity grade and relationship to study treatment. Separate summaries will also be provided for:

- Serious mTEAE regardless of causality,
- Serious mTEAE related to study treatment,
- Serious rTEAE regardless of causality, and
- Serious rTEAE related to study treatment.

Patients with multiple occurrences of events for a given PT, SOC will only be counted once.

Adverse event time-adjusted rates will be calculated as the number of occurrences of event divided by the number of patient-years of treatment-emergent (for the corresponding treatment emergent period)surveillance for each treatment group. Patients can have more than 1 occurrence of each event.

Additionally, Kaplan-Meier methods will be used to display the time to the first Grade 3 or higher TEAE by treatment group. Patients who are not known to have had Grade 3 or higher TEAE by the analysis cutoff date are censored at the date last known to be Grade 3 or higher TEAE-free. Kaplan-Meier methods will also be used to display the time to the first SAE by treatment group. Patients who are not known to have had SAE by the analysis cutoff date are censored at the date last known to be SAE-free.

Subgroup and supplemental tabulations of TEAEs by categorized treatment group, Grade 3 and higher TEAEs by categorized treatment group, and serious TEAEs by categorized treatment group will be created as shown in Table 10.

Group Variable	Subgroups
Study Day Cut Points	0-30 days after initiation of study drug
	1-37 weeks days after initiation of study drug
	>37 weeks after initiation of study drug,
	Denominator for the above categories will be those patients that are on treatment at the beginning of the period.
	Adverse events will be assigned to day categories based on the treatment day of the start date (or worsening date) of the adverse event. Study days after initiation of study drug use the study day computations presented in Section 5.2.5.
Age (years)	<65
	≥65
	<75
	≥75
	<85
	≥85
Baseline Body Mass Index	BMI Underweight: BMI is less than 18.5.
	Normal weight: BMI is 18.5 to 24.9.
	Overweight: BMI is 25 to 29.9.
	Obese: BMI is 30 or more
Geographic Region	North America
	Europe
	Rest of the World
History of Cardiovascular Disease	Yes
-	No

Table 10.Subgroup and Supplemental Tabulations of Treatment-Emergent
Adverse Events (TEAEs)

6.8.2. Deaths

The frequency (number and percentage) of patients in the safety analysis set who died and who died within 30 days after last dose of study treatment as well as the primary reason for death, will be tabulated based on information from 'Survival Follow-Up' CRFs, by treatment arm.

